The additional vital sign measurements added are aligned with PK measurements taken at same timepoints and will add to the evaluation of any potential tachycardia or hypotension.

Change 14: Added exclusion criteria for restricted concomitant medications.

The primary change occurs in Section 7.2 Exclusion Criteria.

Description Added the following exclusion criteria for Groups 1 through 3: **Are unable to refrain** of change: **from or anticipates the use of:**

- **strong CYP3A4 inhibitors or inducers**
- **serotonin agonists or antagonists**
- **monoamine oxidase inhibitors**
- **noradrenergic agonists**
- **selective serotonin reuptake inhibitors**
- **gamma—aminobutyric acid antagonists**
- **N-methyl-D-aspartate receptor antagonists**

beginning approximately 7 days before administration of the trial drug,

throughout the trial, until the Follow-up Visit.

Rationale for Change:

Restricted concomitant medications (in Section [7.3 Excluded Medications, Supplements, and Dietary Products](#) and others added to minimize the risk of serotonin syndrome) were inadvertently omitted from exclusion criteria in the original protocol.

Section [7.3 Excluded Medications, Supplements, and Dietary Products](#) also contains this change.

Amendment 1 to A Phase 1, Non-Randomized, Open-Label Trial to Evaluate the Effect of Hepatic Impairment on the Single Dose Pharmacokinetics of Intravenous TAK-954

ELECTRONIC SIGNATURES

Signed by	Meaning of Signature	Server Date (dd-MMM-yyyy HH:mm 'UTC')
PPD	Clinical Pharmacology Approval	09-Oct-2017 10:57 UTC
	Statistical Approval	09-Oct-2017 13:47 UTC
	Pharmacovigilance Approval	09-Oct-2017 14:23 UTC
	Clinical Science Approval	09-Oct-2017 19:11 UTC

3.0 LIST OF ABBREVIATIONS

AE	adverse event
CCI	
ANOVA	analysis of variance
ANCOVA	analysis of covariance
AUC	area under the concentration-time curve
AUC_∞	area under the concentration-time curve from time 0 to infinity, calculated using the observed value of the last quantifiable concentration
AUC_{last}	area under the concentration-time curve from time 0 to time of the last quantifiable concentration
CI	confidence interval
CL	clearance
CCI	
C_{max}	maximum observed concentration
CPAP	clinical pharmacology analysis plan
CRF	case report form
CV	coefficient of variation
ECG	electrocardiogram
eCRF	electronic case report form
FDA	Food and Drug Administration
CCI	
HR	heart rate
LLN	lower limit of normal
MAV	markedly abnormal value
MedDRA	Medical Dictionary for Regulatory Activities
PGx	pharmacogenomics
PK	pharmacokinetics
PT	Preferred term
PTE	Pretreatment adverse event
QTcF	QT interval with Fridericia correction method
RBC	red blood cell
SAE	serious adverse event
SAP	statistical analysis plan
SD	standard deviation
SOC	System organ class
CCI	
TEAE	treatment-emergent adverse event
WHODrug	World Health Organization Drug Dictionary

4.0 OBJECTIVES

4.1 Primary Objective

The primary objective of the trial is to evaluate the effect of varying degrees of hepatic function on the single dose pharmacokinetics of IV TAK 954.

4.2 Secondary Objective

The secondary objective of the trial is to evaluate the safety and tolerability of single IV doses of TAK 954 in subjects with varying degrees of hepatic function.

4.3 Exploratory Objectives

Exploratory objectives of this trial include:

CCI

4.4 Study Design

This is a phase 1, nonrandomized, open-label trial in males and females (non-childbearing potential) with hepatic impairment and healthy males and females. [Table 4.a](#) displays the number of subjects who will participate in the study based on design options:

Table 4.a Number of Subjects Based on Study Design Options

Group	Number of Subjects	Total Number of Subjects
Reduced Study Design		
Group 1 (Mild)	0	~24
Group 2 (Moderate)	Minimum of 8	
Group 3 (Severe)	Maximum of 8	
Group 4 (Healthy)	Minimum of 8	
Full Study Design		
Group 1 (Mild)	Minimum of 8	~32
Group 2 (Moderate)	Minimum of 8	
Group 3 (Severe)	Maximum of 8	
Group 4 (Healthy)	Minimum of 8	

The groups will be enrolled in a staggered fashion, beginning with Group 2 (Child-Pugh Class B). After safety and PK data are available for 2 subjects in Group 2, dosed at 0.2 mg, Takeda personnel and the investigator will review this data and confirm or modify the TAK-954 dose for the remaining 6 subjects. Enrollment of healthy subjects (Group 4) may begin after the second moderately hepatically-impaired subject (Group 2) is enrolled. As much as possible, the healthy

subjects should be comparable to the hepatic impairment groups with respect to median age and weight (approximately 50% of healthy subjects on each side of the median age and weight of currently enrolled hepatically-impaired subjects grouped together), gender, and race. This will be decided by the investigator in discussion with Takeda. When Group 2 has completed, and following another assessment of PK and safety, Takeda personnel and the investigator will decide whether to enroll subjects in Group 1 (Child-Pugh Class A) or not (reduced vs full trial design). During this review the dose for subjects from Group 1 and/or Group 3 will be selected.

Table 4.b Hepatic Function Categories Based on Child-Pugh Score

Assessment Parameters	Points Scored for Observed Findings (a)		
	1 point	2 points	3 points
Encephalopathy grade (b)	none	1 or 2	3 or 4
Ascites	absence	slight	moderate
Serum bilirubin, mg/dL	<2	2 to 3	>3
Serum albumin, g/dL	>3.5	2.8 to 3.5	<2.8
Prothrombin time, seconds prolonged	<4	4 to 6	>6

Source:

<https://www.fda.gov/downloads/Drugs/GuidanceComplianceRegulatoryInformation/Guidances/ucm072123.pdf>.

(a) Classification of clinical severity:

Mild (Class A): total score 5-6 points.

Moderate (Class B): total score 7-9 points.

Severe (Class C): total score 10-15 points.

(b) Grade 0: normal consciousness, personality, neurological examination, electroencephalogram.

Grade 1: restless, sleep disturbed, irritable/agitated, tremor, impaired handwriting, 5 cycles per second (cps) waves.

Grade 2: lethargic, time-disoriented, inappropriate, asterixis, ataxia, slow triphasic waves.

Grade 3: somnolent, stuporous, place-disoriented, hyperactive reflexes, rigidity, slower waves.

Grade 4: unrousable coma, no personality/behavior, decerebrate, slow 2-3 cps delta activity.

The trial will include a Screening Visit, an in-patient period, and a Follow-up Visit.

Blood for free and total plasma concentration and urine samples for assessment of TAK-954 concentrations will be collected before the start of the TAK-954 infusion and at intervals up to 96 hours after the start of the infusion. Samples may be assayed for TAK-954 metabolites. TAK-954 and its metabolites may also be assayed in urine, data permitting and if deemed possible. Plasma protein binding of TAK-954 will also be assessed.

Whole blood samples for DNA PGx analysis and RNA isolation will be collected predose on Day 1.

Safety will be assessed by monitoring for AEs, ECGs, vital signs, safety laboratory tests, and physical examinations throughout the trial.

After completion of the trial (or after subject withdrawal), all subjects will return for a Follow-up Visit, approximately 10 to 14 days after the dose of trial drug.

5.0 ANALYSIS ENDPOINTS

5.1 Primary Endpoints

The primary endpoints of the trial are the following PK parameters (expressed as total and free):

- Maximum observed concentration (C_{max}).
- Area under the concentration-time curve from time 0 to the last measurable time point, (AUC_{last}).
- Area under the concentration-time curve from time 0 to and extrapolated to infinity (AUC_{∞}).

5.2 Safety Endpoints

Safety endpoints include the following:

[figure not shown]
Safety and tolerability will be assessed through physical examinations, ECGs, vital signs, and clinical laboratory assessments, and collection of spontaneous AEs.

5.3 Exploratory Endpoints

Exploratory endpoints will be assessed through the following parameters:

PK parameters:

CCl

6.0 DETERMINATION OF SAMPLE SIZE

The planned sample size of 8 subjects in each hepatic function group is in line with regulatory guidance for these types of studies (“FDA Guidance for Industry Pharmacokinetics in Patients with Impaired Hepatic Function: Study Design, Data Analysis, and Impact on Dosing and Labeling” and “EMEA Guideline on The Evaluation of the Pharmacokinetics of Medicinal Products in Patients with Impaired Hepatic Function”). The sample size of 8 healthy subjects allows for healthy subjects to be represented for a comparator or reference.

Subjects who drop out may be replaced at the discretion of the sponsor in consultation with the investigator. Subjects who replace dropouts will begin the trial as a new subject.

7.0 METHODS OF ANALYSIS AND PRESENTATION

7.1 General Principles

Continuous data will be summarized using the following: number of subjects (N), mean, standard deviation (SD), median, minimum, and maximum, where appropriate. Where indicated, coefficient of variation (%CV) and geometric mean will also be included in the summary of continuous data. Categorical data will be summarized using the number and percentage of subjects for each category where appropriate.

Unless otherwise stated, Baseline will be defined as last observation prior to administration of the study drug.

All statistical tests will be two-tailed at $\alpha=0.05$ level for significance unless otherwise stated. P-values (when rounded to three digits) less than or equal to α are reported as “significant”. “No statistically significant difference” means that all p-values for the tests are greater than α . All computations will be performed prior to rounding.

In general, the presentation of decimal points will follow the following rules as appropriate: minimum and maximum values will be presented using the same number of decimal places as the recorded data. Arithmetic means, geometric means, and medians will be presented to 1 more decimal place than the recorded data, and SDs will be presented to 2 more decimal places than the recorded data. The confidence interval (CI) for a parameter estimate will be presented using the same number of decimal places as the parameter estimate. Percentage will be presented to 1 decimal place (e.g., 80.1%). All p-values will be rounded to 3 decimal places prior to assessment of statistical significance.

All statistical analyses will be performed using the SAS System[®] Version 9.4 or higher.

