7.9.2 Analysis of Pharmacokinetic Parameters

PK parameters will be compared between normal and hepatically-impaired groups, classified by Child-Pugh Score and summarized descriptively. PK parameters of TAK-954 will be derived using noncompartmental analysis methods and will be determined from the concentration-time data for all evaluable subjects. Actual sampling times, rather than scheduled sampling times, will be used in all PK computations involving sampling times.

The following plasma PK parameters (free and total) for TAK 954 will be calculated:

- C_{\max}
- AUC_{∞}
- AUC_{last}

Specific or additional PK parameters may be added as appropriate per the Clinical Pharmacology Analysis Plan (CPAP).

Descriptive statistics (e.g. mean, standard deviation, standard error, %CV, minimum, median and maximum) will be used to summarize PK parameters (expressed as free and total) according to the hepatic function group (healthy subjects and mild, moderate, severe hepatic impairment). In addition, geometric means will be calculated for C_{max} and AUCs.

All pharmacokinetic parameters will be provided in a data listing.

An analysis of variance (ANOVA) will be performed on log transformed C_{max} , AUCs (total and free) and CL to compare each hepatically-impaired group with the normal hepatic function group and 90% confidence intervals for the ratio of central values from each hepatic impairment group versus normal function group will be provided. In addition, an analysis of covariance (ANCOVA) with hepatic function group as a fixed effect, age, gender and body weight as covariates will be performed on log transformed C_{max} , AUCs (total and free) and CL to investigate effect of covariates on the relationship between TAK-954 PK parameters and level of hepatic impairment. Tests will be performed on all covariates, 0.05 significance level will be used.

In addition, the relationship between Child-Pugh scores, baseline serum bilirubin, serum albumin, prothrombin time and TAK-954 C_{max} , C_{maxu} , AUC_{last} , AUC_{lastu} , AUC_{∞} and $AUC_{\infty u}$ will be evaluated graphically. Regression approaches will be used to evaluate these relationships if appropriate.

Additional analyses will be included, if appropriate. Any deviation from the analysis plan will be reported in the Clinical Study Report.

Individual pharmacokinetic parameter data will be presented in the data listing.

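### SAP 7.1 judges significance on p-values rounded to three decimals, so the working cut-off is 0.0505 rather than the stated 0.05 (very small effect, one-sentence fix)

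*SAP*

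**What the plan says.** SAP 7.1 (General Principles) makes two-tailed testing at alpha = 0.05 the default. It then brings rounding into the decision in two places.

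- The paragraph on testing says "P-values (when rounded to three digits) less than or equal to" alpha are the ones reported as significant. Equality therefore counts.
- The next paragraph, on decimal presentation, ends with "All p-values will be rounded to 3 decimal places prior to assessment of statistical significance".

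The testing paragraph also contains the general statement "All computations will be performed prior to rounding".

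SAP 7.9.2 commits to covariate tests in an ANCOVA of the log-transformed PK parameters, with age, gender and body weight as covariates: "Tests will be performed on all covariates, 0.05 significance level will be used". The comparison of each impaired group with the normal-function group takes a different form: "90% confidence intervals for the ratio of central values from each hepatic impairment group versus normal function group will be provided".

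**The concern.** Rounding for display is harmless. Here the rounding comes before the decision and equality counts, so some p-values above 0.05 are declared significant. No p-value at or below 0.05 is ever lost, because it rounds to 0.050 or less. The error therefore runs in one direction, and the test applied is not exactly the 0.05 test that the SAP states.

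What is at stake is narrow. A covariate whose p-value lies just above 0.0500 and below 0.0505 would be reported as having a significant effect on TAK-954 pharmacokinetics.

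**Working it through.** **Inputs**

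- Level: 0.05, two-tailed (SAP 7.1).
- Decision rule: significant if the p-value, rounded to three decimals, is ≤ 0.05 (SAP 7.1).
- Tests named at this level: the ANCOVA covariates age, gender and body weight (SAP 7.9.2).
- Assumptions for the numerical check: exactly 8 subjects in each enrolled group, and one degree of freedom per covariate. Residual degrees of freedom are then 32 − 4 − 3 = 25 in the full design and 24 − 3 − 3 = 18 in the reduced design.

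**Step 1. The stated figure.** Under the null, the p-value of a continuous test statistic is uniform on (0, 1). Comparing the unrounded p-value with 0.05 gives P(p ≤ 0.05) = 0.0500, which reproduces the stated level.

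**Step 2. The rule as written.** Every p below 0.0505 rounds to 0.050 or less:

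| Unrounded p | Rounded to 3 decimals | Called significant |
|---|---|---|
| 0.0500 | 0.050 | yes |
| 0.05001 | 0.050 | yes |
| 0.0503 | 0.050 | yes |
| 0.05049 | 0.050 | yes |
| 0.0506 | 0.051 | no |

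The size is P(p < 0.0505) = 0.0505. Round-half-up and round-half-even differ only at exactly p = 0.0505, which has probability zero.

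**Step 3. Size of the excess.** 0.0505 − 0.0500 = 0.0005 per test, or 0.05 percentage points. Relative to the stated level this is 0.0005 / 0.05 = 1%.

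**Step 4. Simulation check.** 20 million null t statistics were drawn at each residual df. The Monte Carlo standard error is √(0.05 × 0.95 / 20,000,000) ≈ 0.00005.

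| Residual df | Unrounded rule | SAP rule | Critical abs(t) at 0.0500 | Critical abs(t) at 0.0505 |
|---|---|---|---|---|
| 25 | 0.04997 | 0.05046 | 2.0595 | 2.0547 |
| 18 | 0.05000 | 0.05050 | 2.1009 | 2.0958 |

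Both columns agree with the exact values within simulation error. The critical value moves by about 0.005.

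**Step 5. Context for one PK parameter.** Its three covariate tests, treated as independent for illustration, give at least one false positive with probability 1 − 0.95³ = 14.26% under the unrounded rule and 1 − 0.9495³ = 14.40% under the SAP rule.

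**The case against.** The best defence is that this is a pre-specified and openly stated convention. It leaves the analyst no discretion, and it guarantees that the displayed p-value and the verdict agree. To the two decimals in which alpha is written, 0.0505 and 0.05 are the same number. Nothing important depends on it: the hepatic-group comparisons are interval estimates, the 2.5-fold statement in protocol 11.1.3 uses no p-value, and the sample size in SAP 6.0 rests on regulatory guidance rather than on a power calculation. The point about materiality stands in full. Pre-specification makes the rule transparent, but it does not make it a 0.05 test.

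Three stronger readings are tempting, and the documents do not support them.

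- **That SAP 7.1 contradicts itself.** A reader might set "All computations will be performed prior to rounding" against the rounding rule. The sentences fit together: compute the p-value at full precision, round it, then compare it with alpha.
- **That SAP 7.1 conflicts with 7.9.2.** Section 7.9.2 gives the level for the covariate tests, and 7.1 gives the general way of judging any p-value against a level. A general rule applied to a particular test is not a conflict.
- **That the excess adds up to a meaningful familywise error.** Counting seven parameters (Cmax, AUClast and AUC∞, each total and free, plus CL) by three covariates gives 21 tests. A reader might then compute 1 − 0.9995²¹ ≈ 1.0% as the chance of a call due to rounding alone. The count depends on how far the words on total and free reach in 7.9.2; other readings give 18 to 24 tests. Independence is not plausible either. If CL is dose divided by AUC∞ (which the SAP does not spell out) and all subjects receive the same dose, log CL is a constant minus log AUC∞, and its covariate tests repeat those of AUC∞. The 1.0% is therefore close to the ceiling of 21 × 0.0005 = 1.05%. It is also not the rise in false-positive risk. Under the same assumptions, the chance of any false positive goes from 65.9% to 66.3%, a rise of 0.37 percentage points in a set of tests that was never controlled as a family.

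**Conclusion.** The point holds at minimal severity. As written, SAP 7.1 delivers a level of 0.0505 per test against a stated 0.0500, and the 0.0005 excess always favours significance. This follows from the text and from a continuous test statistic; it does not depend on the degrees of freedom or on the assumed group sizes.

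In practice it touches only the supportive ANCOVA tests of age, gender and body weight, and the regressions that 7.9.2 leaves optional. The primary 90% confidence intervals and the 2.5-fold exposure statement are unaffected. This is a correction to a stated rule, and it should not be read as a threat to the trial's conclusions.

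**What to change.** In SAP 7.1, delete the parenthesis about rounding to three digits from the definition of a significant result, and delete the sentence that places rounding before the assessment of significance. In their place, state: *Significance is judged on the unrounded p-value (p ≤ 0.05). P-values are rounded to three decimals for display only.* This restores a size of 0.0500 per test (simulated 0.0500 at both 25 and 18 df).

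The cost is one sentence of wording, with no new data or analysis. The downside is that a displayed 0.050 may occasionally be non-significant; a fourth decimal or a footnote resolves that. If the SAP is not reissued, the change can be recorded in the Clinical Study Report, where 7.9.2 already provides for reporting deviations from the plan.

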7.1.1 Study Definitions

There are no study-specific definitions.

7.1.2 Definition of Study Days

Study Day 1 is defined as the date of the first dose of study drug, as recorded on the electronic case report form (eCRF) dosing page. Other study days are defined relative to Study Day 1, with Day 1 being Study Day 1 and Day -1 being the day prior to Study Day 1. Study days prior to the first dose of study drug will be calculated as: {date of assessment/event – date of first dose of study drug}. Study days on or after the first dose of study drug will be calculated as: {date of assessment/event – date of first dose of study drug + 1}.

7.1.2 Definition of Study Visit Windows

There will be no visit windowing.

7.1.3 Conventions for Missing Adverse Event Dates

There will be no imputation of incomplete or missing adverse event dates.

7.1.4 Conventions for Missing Concomitant Medication Dates

There will be no imputation of incomplete or missing concomitant medication dates.

7.1.5 Conventions for Missing Data

There will be no imputation of incomplete or missing data. Inclusion of subjects who are noncompliant with the dosing or who have incomplete data, will be made on a case-by-case basis. Plasma or urine concentrations that are below the limit of quantification (< BLQ) will be treated as zero in the summarization of concentration values and derivation of PK parameters. They will be flagged in the data listings; however, deviations from this convention may be considered on a case-by-case basis.

7.2 Analysis Sets

The following analysis sets will be used for analysis and presentation of the study data:

- Safety Set: The safety set will consist of all subjects who are enrolled and receive the study drug. Subjects in this analysis set will be used for demographic, baseline characteristics, and safety summaries.
- Pharmacokinetic (PK) Set: The PK set will consist of all subjects who are enrolled and receive the appropriate dose of trial drug and have at least 1 measurable plasma concentration or amount of drug in the urine for TAK-954. All subjects with valid PK parameter estimates will be included in the summaries and analyses for that parameter. The subjects receive inappropriate dose will not be included in PK set, but the data from those subjects will be listed and flagged.

7.3 Disposition of Subjects

The number and percentage of subjects who are enrolled, complete study drug and study visits, and who prematurely discontinue study drug and/or study visits will be summarized by hepatic function group (healthy subjects, mild, moderate and severe hepatic impairment) and overall. Subjects' study completion data, including reasons for premature termination, will be listed. Additionally, disposition information for screen failures will be listed. A listing of inclusion/exclusion criteria not met will be provided for subjects who did not meet at least one inclusion criterion.

Significant protocol deviations will be listed and summarized.

7.4 Demographic and Other Baseline Characteristics

Demographic and baseline characteristics will be summarized for subjects in the safety set. Summaries will be presented by all subjects and each hepatic function group. Summary statistics (number of subjects (N), mean, SD, median, minimum, and maximum) will be presented for continuous variables (e.g., age, weight, and BMI), and the number and percentage of subjects within each category will be presented for categorical variables (e.g., sex, ethnicity, and race). Individual subject demographic and baseline characteristic data will be provided in the data

listings. In addition, baseline hepatic function parameters and Child-Pugh scores will be summarized by group.

Demographic variables for screen failure subjects and reasons for screen failures will be summarized for subjects who are screened but not enrolled in the study.

There will be no inferential analysis of demographic and baseline characteristics.

